## 9.4 Renal safety monitoring

Renal events are defined as one of the following:

- confirmed (after  $\geq 24$ h) increase in serum creatinine of  $\geq 25\%$  compared to baseline during normal hydration status
- new onset ( $\geq 1+$ ) proteinuria, hematuria or glucosuria; or as a
- doubling in the urinary albumin-creatinine ratio (ACR) or urinary protein-creatinine ratio (PCR) (if applicable).

The following two categories of abnormalities/adverse events have to be considered during the course of the study:

- Serum creatinine triggers that will require follow up and repeat assessments of the abnormal laboratory parameter
- Urine dipstick triggers that will require follow up and repeat assessments of the abnormal laboratory parameter

**Table 9-3 Specific Renal Alert Criteria and Actions**

Renal Event	Actions
Serum creatinine increase 25 – 49% compared to baseline	Confirm 25% increase after 24-48h Follow up within 2-5 days
Serum creatinine increase $\geq 50\%$ compared to baseline	Follow up within 24-48h if possible Consider drug interruption Consider patient hospitalization /specialized treatment
Albumin- or Protein-creatinine ratio increase $\geq 2$ -fold Albumin-creatinine ratio (ACR) $\geq 30$ mg/g or $\geq 3$ mg/mmol; New dipstick proteinuria $\geq 1+$ Protein-creatinine ratio (PCR) $\geq 150$ mg/g or $>15$ mg/mmol	Confirm value after 24-48h Perform urine microscopy Consider drug interruption / discontinuation
New dipstick glucosuria $\geq 1+$ not due to diabetes	Blood glucose (fasting) Perform serum creatinine, ACR
New dipstick hematuria not due to trauma	Urine sediment microscopy Perform serum creatinine, ACR
Document contributing factors: co-medication, other co-morbid conditions, and additional diagnostic procedures performed in the CRF	

Monitor patient regularly (frequency at investigator's discretion) until one of the following:

Event resolution: (sCr within 10% of baseline or protein-creatinine ratio within 50% of baseline)

Event stabilization: sCr level with  $\pm 10\%$  variability over last 6 months or protein-creatinine ratio stabilization at a new level with  $\pm 50\%$  variability over last 6 months.

## **9.5 Pregnancy reporting**

To ensure patient safety, each pregnancy occurring after signing the informed consent must be reported to Novartis within 24 hours of learning of its occurrence. The pregnancy should be followed up to determine outcome, including spontaneous or voluntary termination, details of the birth, and the presence or absence of any birth defects, congenital abnormalities, or maternal and/or newborn complications. The study drug must be discontinued, though the patient may stay in the study, if she wishes to do so. All assessments that are considered as a risk during pregnancy must not be performed. The patients may continue all other protocol assessments.

Pregnancy must be recorded on a Pharmacovigilance Pregnancy Form and reported by the investigator to the local Novartis Drug Safety and Epidemiology Department. Pregnancy follow-up should be recorded on the same form and should include an assessment of the possible relationship to the Novartis study drug of any pregnancy outcome. Any SAE experienced during pregnancy must be reported on an SAE Report Form.

Pregnancy outcomes must be collected for the female partners of any males who took study treatment in this study. Consent to report information regarding these pregnancy outcomes should be obtained from the mother. (Prepare and submit for EC/IRB approval the ICF to cover this with the main study ICFs).

Procedures to be followed in this case are described in the attached link:

[Link to Guideline on Prevention of Pregnancies in Clinical Trials \(go/CSSG\)](#)

## **9.6 Prospective suicidality assessment**

Not applicable.

## **9.7 Early phase safety monitoring**

The Investigator will monitor adverse events in an ongoing manner and inform the Sponsor of any clinically relevant observations. Any required safety reviews will be made jointly between medically qualified personnel representing the Sponsor and Investigator. Such evaluations may occur verbally, but the outcome and key discussion points will be summarized in writing (e-mail) and made available to both Sponsor and all Investigator(s). Criteria pertaining to stopping the study/treatment or adapting the study design are presented above.

When two or more clinical site(s) are participating in the clinical study, the Sponsor will advise the Investigator(s) at all sites in writing (e-mail) (and by telephone if possible) of any new, clinically relevant safety information reported from another site during the conduct of the study in a timely manner.

## **10 Data review and database management**

### **10.1 Site monitoring**

Before study initiation, at a site initiation visit or at an investigator's meeting, a Novartis representative will review the protocol and CRFs with the investigators and their staff. During the study Novartis employs several methods of ensuring protocol and GCP compliance and the quality/integrity of the sites' data. The monitor will visit the site to check the completeness of patients records, the accuracy of entries on the CRFs, the adherence to the protocol and to Good Clinical Practice, the progress of enrollment, and to ensure that study drug is being stored, dispensed, and accounted for according to specifications. Key study personnel must be available to assist the monitor during these visits.

### **10.2 Data collection**

Designated investigator staff will enter the data required by the protocol into the Electronic Case Report Forms using fully validated software that conforms to 21 CFR Part 11 requirements. Designated investigator site staff will not be given access to the EDC system until they have been trained. Automatic validation programs check for data discrepancies and, by generating appropriate error messages, allow the data to be confirmed or corrected before transfer of the data to CMED clinical database, Timaeus. The Investigator must certify that the data entered into the Electronic Case Report Forms are complete and accurate. After database lock, the investigator will receive a CD-ROM or paper copies of the subject data for archiving at the investigational site.

Data not requiring a separate written record will be defined in the Site Operations Manual and assessment schedule and can be recorded directly on the CRFs. All other data captured for this study will have an external originating source (either written or electronic) with the CRF not being considered as source.

### **10.3 Database management and quality control**

All data should be recorded, handled and stored in a way that allows its accurate reporting, interpretation and verification.

CMED Data Management review the data entered into the eCRFs by investigational staff for completeness and accuracy and instruct the site personnel to make any required corrections or additions. Queries are sent to the investigational site using an electronic data query. Designated investigator site staff is required to respond to the query and confirm or correct the data.

Concomitant medications entered into the database will be coded using the WHO Drug Reference List, which employs the Anatomical Therapeutic Chemical classification system. Medical history/current medical conditions and adverse events will be coded using the Medical dictionary for regulatory activities (MedDRA) terminology.

Select laboratory samples will be processed centrally and the results will be sent electronically to Novartis (or a designated CRO)

### **Corporate Confidential Information**

Holter data will be processed centrally and results will be sent electronically to Novartis (or designated CRO).

For echocardiograms, a dedicated imaging CRO will collect all echo data from the sites and send for quantitative analysis to a blinded expert reader. The analysis results will then be collected by the imaging CRO and transformed into a Novartis format defined by a data transfer specification. The transformed output will then be sent to Novartis data management for incorporation into the Clinical Study Report (CSR). The imaging CRO will be responsible for all image data clarification forms and missing data at all sites.

At the conclusion of the study, the occurrence of any emergency code breaks will be determined after return of all code break reports and unused drug supplies to Novartis.

### **Corporate Confidential Information**

#### **10.4 Data Monitoring Committee**

Not required.

#### **10.5 Adjudication Committee**

Not required

### **11 Data analysis**

Data analyses will be conducted under the supervision of Novartis personnel.

#### **11.1 Analysis sets**

For all analysis sets, subjects will be analyzed according to the study treatment(s) received.

The full analysis set will include all subjects that received any study drug or placebo.

The safety analysis set will be the same as the full analysis set.

The primary PK analysis set will include all subjects with available PK data. The secondary PK analysis set will include all subjects with available PK data and no protocol deviations with relevant impact on PK data.

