### 2.2 Secondary objective(s)

Secondary objective(s)	Endpoints related to secondary objective(s)

To determine the pharmacokinetics of CLR325, and the active metabolite, CQJ295, during an 18-hour i.v. infusion of CLR325 in heart failure patients.

	

Plasma and urine pharmacokinetic parameters of CLR325 and CQJ295 (Cmax, Tmax, AUC0-18h, AUClast, AUC0-28h, AUCinf, T1/2, CL (CLR325 only), Vss (CLR325 only), CLr, and Ae0-28 during the course of an 18-hour infusion and post-infusion in heart failure patients.

To determine the immunogenicity of an 18-hour i.v. infusion of CLR325 in heart failure patients.

	

Treatment related titer of anti-CLR325 and anti-apelin antibodies after infusion of CLR325 in heart failure patients.

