### **6.3 Permitted dose adjustments and interruptions of study treatment**

Should there be any technical problems with the infusion line (i.e. infiltration, infusion pump malfunction) the infusion must be restarted within 30 minutes or the patient will be considered discontinued from treatment and the infusion shall not be restarted.

Dosage may be discontinued if required to address any safety concerns and should not be restarted. Dose adjustments of study treatment will not be permitted.

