# **7 Discontinuation and study completion**

## **7.1 Discontinuation of study treatment**

Patients may voluntarily discontinue study treatment for any reason at any time.

The investigator must discontinue study treatment for a given patient if, on balance, he/she believes that continuation would be detrimental to the patient's well-being.

Study treatment must be discontinued under any of the following circumstances:

- Patient withdraws consent
- Any protocol deviation that results in a significant risk to the subject's safety
- Emergence of the following adverse events:
  - Acute myocardial infarction
  - Worsening myocardial ischemia
  - Sustained atrial or ventricular tachycardia
  - AICD discharge or anti-tachycardia pacing by the AICD in a patient with an AICD in place
  - An increase in non-sustained ventricular tachycardia or ventricular ectopy deemed clinically concerning by the investigator
  - Severe allergic reaction (e.g., angioedema)
- Occurrence of persistent elevation of systolic blood pressure to >180 mmHg or diastolic blood pressure >100 mm Hg
- Occurrence of symptomatic hypotension requiring persistent medical intervention (i.e. fluid replacement or inotropic therapy). Note that change of patient position does not qualify as an intervention if the need for this change in position is not persistent
- A drop in cardiac index of > 30% as compared to the average of all cardiac index measurements obtained prior to the start of infusion. All cardiac index values showing a 30% drop from baseline should be repeated and study drug terminated only if values are confirmed.
- Any clinically significant cardiac arrhythmia resulting in hemodynamic instability or requiring medical intervention to terminate
- Any of the following laboratory abnormalities:
  - Elevation in white blood cell count to greater than 2.5x above the ULN
  - Elevated AST or ALT > 8x above the ULN
  - Elevated AST or ALT > 3x above the ULN and TBL > 2x the ULN but without an increase in ALP to >2x the ULN
  - Elevated AST or ALT > 3x above the ULN and symptoms of malaise, fatigue, abdominal pain, nausea, vomiting, or rash with eosinophilia.

The appropriate personnel from the site and Novartis will assess whether study treatment should be discontinued for any patient whose treatment code has been broken inadvertently for any reason.

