#### **7.4 Study Stopping rules**

The study will be paused and no further dosing will be conducted pending a full, unblinded safety review if any of the following criteria are met:

- One or more SAE's are reported
- If 2 or more patients experience an AE that is similar and of severe grade
- If 2 or more patients have their infusion discontinued for safety or tolerability reasons
- A CLR325-treated patient develops anti-apelin antibodies
- The principal investigator and the sponsor consider that the number and/or severity of adverse events justify discontinuation of the study
- The sponsor unilaterally requests it

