### **11.3 Treatments (study drug, rescue medication, other concomitant therapies, compliance)**

Data for total dose of infusion, infusion rate and total time of infusion will be listed by treatment group and subject.

Data for concomitant therapies will be listed by treatment group and subject.

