#### **11.4.2 Statistical model, hypothesis, and method of analysis**

All information obtained on adverse events will be displayed by treatment and subject.

The number and percentage of subjects with adverse events will be tabulated by body system and preferred term with a breakdown by treatment. A subject with multiple adverse events within a body system is only counted once towards the total of this body system.

The occurrence of adverse events will be examined by treatment. Both the total number of adverse events, and the preferred term for the adverse event will be compared by treatment group.

It is hypothesized that the estimated rate of serious adverse events in the treated group equal to that in the placebo group. The estimated probability of serious adverse events will be examined with 90% confidence limits around the estimated probability. Summary tables with the number, percentage, and severity of adverse events will be provided to assess safety and tolerability per treatment groups. The number and percentage of patients with adverse events will be tabulated by body system and preferred term with a breakdown by treatment group. The difference in the occurrence of adverse effects will be quantified by using the Fisher's Exact Test. Separate tables and listings will be presented indicating event severity and study drug relationship. All safety laboratory and other continuous data will be listed, and descriptive statistics will be generated.

All data for vital signs, cardiac monitoring, ECG evaluations, hematology, blood chemistry and urinalysis will be listed for each subject and summarized by descriptive statistics per treatment and for time interval where appropriate. For all these safety variables, if ranges are available, abnormalities will be flagged. The individual data and descriptive statistics will be also shown as graphical outputs. Cardiac monitoring data will be listed and descriptive statistics generated by treatment and time. Graphical presentations will be generated to show the individual time course of the data, including concentration-response plots.

Pharmacokinetic results will be summarized by descriptive statistics per treatment.

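### Do the PK analysis sets distort the AUC and urinary excretion summaries by mixing shortened infusions with full 18-hour ones?

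*Protocol*

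**What the plan says.** Section 11.1 defines two PK sets. For the first: "The primary PK analysis set will include all subjects with available PK data". For the second: "The secondary PK analysis set will include all subjects with available PK data and no protocol deviations with relevant impact on PK data". Neither definition mentions whether the infusion was completed. The same section analyses subjects by the treatment they received.

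Section 2.2 lists the secondary PK parameters, among them AUC0-18h, AUC0-28h, AUCinf and Ae0-28, as those "during the course of an 18-hour infusion and post-infusion in heart failure patients". Section 11.4.2 adds: "Pharmacokinetic results will be summarized by descriptive statistics per treatment". Section 11.5.3 specifies arithmetic and geometric mean, SD, CV, median, minimum and maximum, and lists the PK parameters by treatment and subject.

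The protocol foresees early stops. Under section 6.3, if the infusion is not restarted within 30 minutes of a technical failure, "the patient will be considered discontinued from treatment and the infusion shall not be restarted". Section 7.1 opens its list of mandatory stops with "Study treatment must be discontinued under any of the following circumstances". Section 7.4 has a study-level criterion: "If 2 or more patients have their infusion discontinued for safety or tolerability reasons". Section 11.3 covers the dosing record: "Data for total dose of infusion, infusion rate and total time of infusion will be listed by treatment group and subject".

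**The concern.** The endpoints describe an 18-hour infusion, but the primary PK set also admits profiles from shorter ones. A stop that section 6.3 or 7.1 orders is compliant conduct. On a plain reading it is therefore not a protocol deviation, and the secondary set may not remove it either.

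Cohorts have only four to six active patients (section 11.6), so one short profile is not diluted. The mean AUC and Ae for a dose would then sit below what a full infusion delivers, and the CV would be inflated. A reader who used those means to describe exposure at that dose would be working from a figure that is too low. The section 7.4 criterion on stopped infusions needs at least two of them, so a single stop would not prompt a review through that route.

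**Working it through.** **Inputs**
- Active patients per cohort: 6 or 4 (section 11.6). The protocol's own figures there concern event detection and do not bear on this point, but they confirm the cohort sizes: 1 − 0.8^6 = 0.738 (stated 74%) and 1 − 0.8^4 = 0.590 (stated 60%).
- Half-life: section 4.2, criterion 6, equates 10 hours with five terminal half-lives, so 10 / 5 = 2 h and k = ln 2 / 2 = 0.3466 per hour.
- Stop times: the protocol gives none, so 3 to 15 h are assumed.
- Model (assumed): one compartment, constant-rate infusion, linear clearance. Ae0-28 is taken as proportional to AUC0-28h, which means constant renal clearance.

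**One patient's ratio to a full infusion.** With input rate and clearance both set to 1, for an infusion ending at T and t ≥ T:

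AUC(0–t) = T − (1 − e^(−kT))/k + [(1 − e^(−kT))/k] × (1 − e^(−k(t−T)))

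For a stop at 6 h:
- AUC0-18h: 5.961 / 15.120 = 0.394
- AUC0-28h: 5.999 / 17.910 = 0.335
- Cmax: (1 − 2^(−3)) / (1 − 2^(−9)) = 0.877

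**Shift in the summary.** With one of n patients stopped and ratio r, the arithmetic mean changes by (n − 1 + r)/n − 1 and the geometric mean by r^(1/n) − 1. For n = 6:

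| Stop at | r, AUC0-18h | arithmetic / geometric | r, AUC0-28h and Ae0-28 | arithmetic / geometric |
|---|---|---|---|---|
| 3 h | 0.198 | −13% / −24% | 0.167 | −14% / −26% |
| 6 h | 0.394 | −10% / −14% | 0.335 | −11% / −17% |
| 9 h | 0.587 | −7% / −8% | 0.502 | −8% / −11% |
| 12 h | 0.770 | −4% / −4% | 0.669 | −6% / −7% |
| 15 h | 0.925 | −1% / −1% | 0.836 | −3% / −3% |

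With one of 4 stopped at 6 h, the arithmetic means fall by 15% (AUC0-18h) and 17% (AUC0-28h). Half-lives of 1 to 4 h move the six-patient arithmetic results by about one point or less.

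**What is not affected.** For a stop at 6 h the mean Cmax falls by only 1 − (5 + 0.877)/6 = 2.1%. CL, Vss and half-life are not biased by truncation if the actual dose is used. AUC0-28h per unit of dose delivered is almost unchanged: 0.335 × 18/6 = 1.005.

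**How likely.** The protocol gives no rate of early stops. At assumed rates of 5%, 10% and 20% per patient, the chance of at least one among six is 1 − 0.95^6 = 26%, 1 − 0.90^6 = 47% and 1 − 0.80^6 = 74%.

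**Would excluding stopped patients be better?** Take n = 6, an assumed CV of 30%, and suppose the patient with the highest exposure stops at 6 h. In simulation the pooled mean AUC0-28h is 84.3% of the full-infusion mean, and the completers-only mean is 91.7%. Dropping the patient leaves a bias of its own, so the all-subjects set is not the wrong choice.

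**The case for a change.** The strongest argument for a change is that the protocol is not silent here. It positively defines both sets and the per-treatment summary, and those definitions do not match an endpoint framed on 18 hours. The remedy would be cheap: a few sentences and one more table, with no new data. The text and the arithmetic behind this argument stand.

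Several things weaken it.

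- **Both sets is not established.** The protocol does not say what counts as a deviation with relevant PK impact. A line failure that misses the 30-minute limit in section 6.3 could be classed as one, and one of the section 7.1 triggers is itself a protocol deviation. Redacted text also follows section 11.1.
- **Some values may be missing rather than low.** Section 7.1 asks patients who stop treatment to return for the end-of-study assessments. It does not clearly require plasma sampling and urine collection to hour 28, which the figures above assume. AUClast, and Ae where urine was collected, would still be low.
- **The metabolite is not covered.** The same endpoints apply to CQJ295, whose half-life is not given.
- **Exposure received is a legitimate target** in a non-confirmatory safety study that analyses by treatment received.
- **The case would be visible.** Dose, infusion time and PK parameters are listed by subject. The planned minimum and CV would also tend to show it: with the assumed true CV of 30%, one stop at 6 h raises the mean sample CV of AUC0-28h from 28% to 42%.

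**Conclusion.** The concern is right in direction and does not call for a change. If an active patient's infusion ends early and PK data are available, the primary PK set pools that profile with full infusions. The mean AUC0-28h and Ae0-28 then fall by about 3% to 14% with one of six stopped between 15 and 3 hours. That range rests on assumed stop times, one-compartment linear kinetics, a 2-hour half-life and sampling to hour 28. With no early stop it is zero.

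The primary set would stay as it is even if the point were accepted, because a completers-only set carries selection of its own. What remains is a request for flags, a separate display and dose-normalised summaries. Those are table-level choices that normally belong in the statistical analysis plan, and nothing in the protocol prevents them. The dose delivered and the infusion time needed to make them are already recorded and listed. PK is secondary and descriptive here, so an analyst who meets a truncated profile has what is needed to present it sensibly. Whether an incomplete infusion counts as a PK-relevant deviation is unstated, but analysts can settle that when they classify deviations.

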## **Corporate Confidential Information**

### **11.2 Subject demographics and other baseline characteristics**

All data for background and demographic variables will be listed by treatment group and subject. Summary statistics will be provided by treatment group.

Relevant medical history, current medical conditions, results of laboratory screens, drug tests and any other relevant information will be listed by treatment group and subject.

